## 5.2 Discontinuation of Patients from the Study

Discontinued patients will include both, patients who withdraw from the study (patient's decision) and patients who are discontinued from the study by the decision of the Investigator. A patient can only be discontinued from the study after enrollment.

### Confidentiality Statement

---

Data and information contained in this document are considered to constitute trade secrets and confidential commercial information, and the legal protections provided to such trade secrets and confidential information are hereby claimed under the applicable provisions of applicable law. No part of this document may be publicly disclosed without the written consent of Philip Morris Products S.A.

---

Patients will be informed that they are free to withdraw from the study at any time. Patients should be questioned for the reason of withdrawal from the study, although they are not obliged to disclose it.

If the patient withdraws from the study, he/she will be asked to perform the early termination procedures (section 9.6) as soon as possible after the time of withdrawal unless the patient refuses to do it in writing.

If a patient expressed his/her wish to quit the study during a visit planned for clinical assessment, he/she will be asked whether he/she would agree to still do the dental/clinical assessments planned for this visit, but with no obligation.

After the time of withdrawal, the patient will enter into the 7-day period of safety follow-up.

#### Discontinuation from the study

Patients must be discontinued from the study for any of the following reasons:

1. Withdrawal of informed consent.
2. Discontinuation is considered to be in the interest of the patient from a safety perspective as judged by the Investigator
3. Positive or unclear pregnancy test.
4. The Sponsor or Investigator terminates the study or the study terminates at a particular investigational site. If the Sponsor or the Investigator decides to prematurely terminate the study, the patient will be promptly informed. The head of the medical institution should report the fact and the reason in writing to the IRB.
5. Patient has to undergo periodontal surgery (as per dentist's decision).
6. Patient becomes an employee of the investigational site or any other parties involved in the study.
7. Lost to follow-up.

Patients may be discontinued from the study for the following reasons:

1. Non-compliance to the study procedures based on the judgment of the Investigator.
2. Patient needs to take systemic antibiotic treatment for any medical condition other than periodontitis, for more than 2 consecutive weeks, during the course of the study.
3. Patient needs to take systemic or topical (in the mouth) antibiotic for more than 5 consecutive days for acute inflammation of periodontitis.

#### **Confidentiality Statement**

---

Data and information contained in this document are considered to constitute trade secrets and confidential commercial information, and the legal protections provided to such trade secrets and confidential information are hereby claimed under the applicable provisions of applicable law. No part of this document may be publicly disclosed without the written consent of Philip Morris Products S.A.

---

4. Patient needs to take systemic steroidal or non-steroidal anti-inflammatory drugs for more than 6 consecutive days
5. Patient needs to take bisphosphonates or anti-coagulants.
6. The number of patients in each randomization stratum has been reached before patient reached V2.

### 5.2.1 Violation of Selection Criteria

Patients who violate the entry criteria prior to enrollment will be considered as screen failures. Re-screening of patients will not be permitted. If a violation of selection criteria is detected after enrollment, patients might be discontinued from the study based on a case-by-case decision of the Investigator.

### 5.2.2 Other Reasons for Discontinuation of Patients from the Study

<NA>

## 5.3 Lost to Follow-up

The date of the last contact with the patient (*e.g.*, last visit, last phone call) should be recorded in the source document.

After the last contact, reasonable number of attempts to contact the patient (including written correspondence and phone calls) should be done and documented in the source documents by the site.

Following the contact attempts, if the Investigator(s) or designee(s) decides to discontinue the patient with the reason of lost to follow-up, the discontinuation date will be recorded. The discontinuation date for the patient will be the date the patient was determined to be lost to follow-up and will correspond to the date of the EOS of the patient.

If the site has lost track of the patient, the discontinuation date cannot exceed the maximum number of study weeks (*i.e.*, 31 weeks), then the Investigator(s) or designee(s) will discontinue the patient with reason as lost to follow-up.

## 6 INVESTIGATIONAL PRODUCT(S)

### 6.1 Description of Investigational Product(s)

#### 6.1.1 Test Product(s)

The product tested in this study is the Tobacco Heating System with Marlboro Heatsticks, marketed in Japan under the brand name IQOS and referred to as IQOS in this protocol. All versions of IQOS and Marlboro Heatsticks available for sale in Japan at the time of study start or becoming available during the course of the study are allowed to be used in the context of this study. The IQOS is composed of the following components: a tobacco *HeatStick*, a Holder and a Charger (Table 1), as well as a cleaning tool, a power supply, and a USB cable (see information on the user guide in Appendix 3):

**Table 1 Test Product (IQOS)**

HeatStick:	
The HeatStick is designed to function with the Holder. The HeatStick is made up of: tobacco plug, hollow acetate tube, polymer-film filter, mouth piece filter, outer and mouth-end papers.
 
All materials have been evaluated with regards to their toxicological potential and have been approved for use.
 
The tobacco plug is made from tobacco, glycerin, water, guar gum, cellulose, propylene glycol, natural and artificial flavorings.
 
The average amount of nicotine in the tobacco plug is 5-6 mg/stick per HeatStick.

Holder:	
The Holder is a slim electrical heating unit that heats the HeatStick in a controlled manner by using a heater blade.
 
The Holder stores enough energy for a single experience, delivering puffs over a period of about 6 minutes or 14 puffs (whichever comes first). A Light Emitting Diode indicates the end of the experience.
 
Once this cycle is complete, the Holder must be recharged before a new HeatStick can be used.

Charger:	
The power supply for the Holder is the Charger.
 
The Charger holds enough energy for approximately 20 uses of the Holder and can be recharged from household power.
 
The Charger stores the Holder when not in use, and provides a secure environment for the cleaning process of the heater blade.

The overall objective of the product design is to provide an acceptable experience in which the HPHCs levels in the aerosol are substantially reduced in comparison with the smoke of a

#### Confidentiality Statement

Data and information contained in this document are considered to constitute trade secrets and confidential commercial information, and the legal protections provided to such trade secrets and confidential information are hereby claimed under the applicable provisions of applicable law. No part of this document may be publicly disclosed without the written consent of Philip Morris Products S.A.

cigarette [95, 96]. A summary of description of the product, pre-clinical and clinical data available on IQOS is provided in the SPI [81].

### 6.1.2 Reference and Baseline Product(s)

Cigarette arm (reference product): patient's own preferred brand of commercially available cigarettes will not be provided by the Sponsor but purchased by the patients for their own use for the duration of the study.

### 6.1.3 Packaging and Labeling

An IQOS starter kit (*i.e.*, IQOS device and a selection of *HeatSticks* flavor variants available on the Japanese market) will be supplied to the site by the Sponsor or authorized representative in packages that protect against deterioration during transport and storage.

The Sponsor or authorized representative will label in local language the IQOS starter kit ensuring adherence to local regulatory and requirements. This will include at least the following information:

- Statement 'For investigational use only'
- Name and address of the Sponsor (if the sponsor resides outside Japan, name of the sponsor and name of the country where the sponsor is located, and name and address of the clinical trial in-country representative)
- IQOS device serial number

## 6.2 Administration of Investigational Product(s)

The study is designed as an *ad libitum* use study. The patients will be allowed to use their allocated products (cigarette or IQOS) according to their need. Patients should be advised that when smoking cigarette or using IQOS, they should temporarily stop using the products in the event of any signs suggesting nicotine overexposure, (*e.g.*, gastrointestinal disturbance [nausea, vomiting, diarrhea, stomach or abdominal pain], cold sweats, headache, dizziness, breathing problems) or any reasons at the discretion of the Investigator.

Any patient who wish to stop smoking during the study will be encouraged to do so and referred to their General Practitioner for a smoking cessation program. This will not lead to discontinuation.

### 6.2.1 From Enrollment to Randomization

From screening visit (V1) to randomization (V2), all patients will be allowed to continue smoking *ad libitum* their preferred usual brand of cigarettes. After randomization all patients will purchase their product, as it will not be provided by the Sponsor.

### Confidentiality Statement

---

Data and information contained in this document are considered to constitute trade secrets and confidential commercial information, and the legal protections provided to such trade secrets and confidential information are hereby claimed under the applicable provisions of applicable law. No part of this document may be publicly disclosed without the written consent of Philip Morris Products S.A.

---

At randomization, patients allocated to the IQOS arm will be supplied with an IQOS starter kit (*i.e.*, IQOS device and a selection of *HeatStick* flavor variants available on the Japanese market) but thereafter they will have purchase their own *HeatSticks* for use during the study.

## 6.2.2 Investigational Period

### 6.2.2.1 IQOS Arm

IQOS arm: patients randomized to the IQOS arm will be instructed to use exclusively IQOS *ad libitum*. The switch to different flavors of *HeatSticks* as well as the use of other tobacco- or nicotine-containing products will not lead to discontinuation.

### 6.2.2.2 Cigarette Arm

Cigarette arm: patients randomized to the cigarettes arm will be instructed to continue smoking their cigarettes *ad libitum*. The switch to different cigarette brands and the use of other tobacco- or nicotine-containing products will not lead to discontinuation.

## 6.2.3 Safety Follow-up Period

During the safety follow-up period (*i.e.*, after the time of V4 or prematurely discontinued), all patients will be free to smoke their own cigarettes, or any other product of their choice.

## 6.3 Method for Assigning Patients to Study Arms

After all assessments of V1 have been completed, patients will be randomized to 1 of the 2 study arms; continued cigarette smoking or IQOS use. Patients will be informed about their study arm allocation at V2. Randomization will be done through the Interactive Web and Voice Response System (IXRS) at any time during the visit. Patients will be randomized in one of the two study arms, IQOS arm:cigarette arm in a 1:1 ratio using a stratified randomization (based on daily cigarette consumption over the month (30 days) prior to V1 (10-19 cigarettes/day vs. >19 cigarettes/day), and disease severity (< 5 mm PD vs.  $\geq$  5 mm PD) in smokers with generalized chronic periodontitis. Disease severity is based on the tooth site having the most severe condition of PD [78]. In each arm, a quota will be applied to ensure that patients with PD  $\geq$  5 mm represent at least 50% of the randomized patients. Arm assignment for patients with PD < 5 mm will be capped at n = 80, after which enrollment of patients with PD < 5 mm will be stopped. Patients with PD < 5 mm already enrolled but not randomized may be discontinued in order to ensure that randomization quota are met. Enrollment of patients with PD  $\geq$  5 mm will continue until 172 patients are randomized. At this stage, patients' enrollment will be stopped and patients already enrolled but not randomized may be discontinued. In case patients are discontinued after V1, they will be referred to their dentist/general practitioner and will receive financial compensation for the

### Confidentiality Statement

---

Data and information contained in this document are considered to constitute trade secrets and confidential commercial information, and the legal protections provided to such trade secrets and confidential information are hereby claimed under the applicable provisions of applicable law. No part of this document may be publicly disclosed without the written consent of Philip Morris Products S.A.

---

visit. Patients will be informed of their randomized study arm by the study site during V2. All patients will be instructed to use their assigned product until they complete the study.

## 6.4 Blinding

### 6.4.1 Blinding of the Examiner

This is an open-label study, however, in order to avoid potential involuntary bias of the examiner by the smoking status, he/she will be kept blinded to the patient arm after randomization. In order to enforce the blinding, the examiner will wear a prescribed mask to avoid noticing the odor, during the full periodontal examination at 3 and 6 months. The blinded examiner should avoid contact with the patient outside of the required full periodontal examinations. In addition, the patients will be asked to wash their hands. If the examiner should become unblinded for any reason, including accidental disclosure, the unblinding event will be documented by the Investigator in a specific log kept in the Site Investigator File. A patient-specific unblinding event will not lead to discontinuation of the patient and will not prevent the use of the patient's data, including those recorded after disclosure.

If a designee needs to perform the periodontal assessments, he/she needs to have been trained on the PD and CAL probing before doing it, *i.e.*, by an examiner who attended the calibration session (section 10.2.1). This needs to be described in the back-up plan that will be provided by the sites (section 10.2.1). The blinding status of the designee will be described in the specific log for blinding.

### 6.4.2 Blinding of Data

There will be additional, even though limited, degree of blinding during the conduct of the study, including the data review and data analysis process. In particular, PMI and contract research organization (CRO) personnel will be as summarized in Table 2:

**Table 2 Blinding Scheme**

Blinded Study Personnel	Blinded Data	End of Blinding Period
PMI and CRO study statisticians	Patient randomization arm and actual values of CAL and PD values after randomization	After the SAP finalization or database lock, whichever comes last.
PMI clinical scientist	Patient randomization arm and actual values of CAL and PD values after randomization	After the finalization of PMI blind database review. Can be actively un-blinded when appropriate.

### Confidentiality Statement

Data and information contained in this document are considered to constitute trade secrets and confidential commercial information, and the legal protections provided to such trade secrets and confidential information are hereby claimed under the applicable provisions of applicable law. No part of this document may be publicly disclosed without the written consent of Philip Morris Products S.A.

Any PMI and CRO personnel who are not listed in the above Table 2 will be unblinded by default.

Unblinded information will not be shared with the blinded study team, until the end of the blinding period (Table 2). PMI will receive blinded and unblinded data for the pre-analysis data review as planned in the data review plan. Blinded data will be accessible by the blinded study personnel in a masked format or presented independent of the patient identifier so to ensure that data cannot be associated within or to a patient. Unblinded data will only be reviewed by the unblinded study team.

## 6.5 Investigational Product Accountability and Adherence

### 6.5.1 Dispensing Investigational Product

Patients allocated to IQOS arm will be supplied with an IQOS starter kit (IQOS device and a selection of *HeatStick* flavor variants available on the Japanese market) at the randomization visit (V2), but will be asked to buy his/her flavor of choice of *HeatSticks* for his/her own use for the entire duration of the study. In case the device needs replacement due to a device malfunction or in case of loss/theft of the device, the patient will need to contact his/her site. In case a patient decides to purchase their own device, these will not be replaced by the site.

Patients allocated to cigarette arm will buy cigarettes for their own use for the entire duration of the study.

### 6.5.2 Storage and Accountability

The study collaborator (the investigational product (IP) storage manager) designated by the head of the investigational site will be responsible for the storage and accountability of the IQOS devices and *HeatSticks* to be distributed only once at V2, together with the device. The IQOS devices (charger and holder) as well as *HeatSticks* (to be distributed only once at V2, together with the device) will be stored in a secured storage site with access limited to authorized personnel only. Because cigarettes will be bought by the patients, cigarettes will not be stored at site. As for *HeatSticks*, a sufficient number of packs will be stored at site, to be delivered with the initial hand out of the IQOS device to patients allocated to the IQOS arm only. A few additional devices will be stored in case a patient needs to have his/her IQOS device replaced. Full accountability of the distributed IQOS starter kit and replacement devices, if any, will be ensured by the designated IP storage manager and recorded in IP accountability logs. This includes but is not limited to the record of the device serial number, *HeatSticks* batch number, the quantity of devices and *HeatStick* packs delivered per patient, date of delivery, total quantity available at site, the quantity of devices returned to the site at the end of the study.

### Confidentiality Statement

---

Data and information contained in this document are considered to constitute trade secrets and confidential commercial information, and the legal protections provided to such trade secrets and confidential information are hereby claimed under the applicable provisions of applicable law. No part of this document may be publicly disclosed without the written consent of Philip Morris Products S.A.

---

Except for the initial packs of *HeatSticks* delivered together with the IQOS device at V2, neither *HeatSticks* nor cigarettes will be stored at site during the study as they will be bought by the patients throughout the study.

### 6.5.3 Investigational Product Retention

The patients will return the IQOS device, including replacement devices to the study site upon early discontinuation or at V4. The study site will return to the Sponsor or authorized representative the IQOS product components upon study completion. This does not apply to devices purchased by the patients.

### 6.5.4 Adherence to Investigational Product(s)

Adherence to the allocated product will be monitored using a questionnaire on self-reported current tobacco and nicotine containing tobacco product consumption (including frequency and quantity of product use) over the past month (section 7.5.7).

### 6.5.5 Product Use Restrictions

There will be no restriction on allocated product use.

### 6.5.6 Dietary Restrictions

From V2 to V4, patients will be asked not to drink, eat, chew gum, use mouth rinse or brush their teeth for at least 30 minutes before collection of oral samples (*i.e.*, SP, GCF or buccal swabs).

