### **Confidentiality Statement**

---

Data and information contained in this document are considered to constitute trade secrets and confidential commercial information, and the legal protections provided to such trade secrets and confidential information are hereby claimed under the applicable provisions of applicable law. No part of this document may be publicly disclosed without the written consent of Philip Morris Products S.A.

---

probably due to the vasoconstrictive action of nicotine on gingival vessels. Because IQOS delivers nicotine, but much reduced levels of other HPHCs, this study may help to differentiate the effects of nicotine vs the effects of HPHCs. To investigate this, it is planned to collect 1) GCF samples, to measure inflammatory components of this oral fluid when switching to IQOS compared to continuing using cigarettes, 2) buccal swabs, to perform an RNA profiling of those cells which are directly exposed to cigarette smoke or IQOS aerosol; and 3) SP samples, to assess the change of the oral microbiome when switching to IQOS compared to patients continuing using cigarettes. The analyses of GCF and buccal swabs will help to better understand the underlying mechanism of the diseases related to cigarette smoke.

The study will follow a two parallel arm randomization design with the following strata: 1) daily cigarette consumption over the month prior to V1 and 2) PD in smokers with generalized chronic periodontitis [78]. This selection is based on the fact that: 1) the degree of smoking exposure is related to the severity of periodontal destruction [25, 82] 2) pre-treatment depth of PD and CAL have been shown to affect response of therapy [83, 84].

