#### Confidentiality Statement

---

Data and information contained in this document are considered to constitute trade secrets and confidential commercial information, and the legal protections provided to such trade secrets and confidential information are hereby claimed under the applicable provisions of applicable law. No part of this document may be publicly disclosed without the written consent of Philip Morris Products S.A.

---

to nicotine exposure. Spot-urine collection will be performed, and the BoExp levels will be adjusted to creatinine to adjust urinary excretion rates.

This study is designed as an *ad libitum* study without product use restriction in order to mimic as closely as possible “real life” condition.

All patients will be asked to buy their own cigarettes or *HeatSticks*, according to their needs for the study, in order to minimize any changes in their smoking behavior, and to not promote one product over the other.

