## 4.2 Appropriateness of Measurements

All dental variables to be measured in this study were selected based on the following criteria: 1) commonly assessed by dentists; 2) acceptability by patients; 3) robustness of the method (*i.e.*, index or evaluation criteria are available to assess improvement of periodontal disease); 4) clinical relevance to support the objectives of the study.

Blinding of the examiners is planned to reduce the potential bias of the periodontal assessments that could be introduced by the smell of tobacco on patients using cigarettes, which is not present on patients using IQOS. Blinding was applied in studies by Preber and Bergstrom [90], Liu and Hwan [46], Rosa et al. [44] and Nair et al. [33]. If the examiner gets unblinded, this will be reported by the Investigator, but the patient will not be discontinued. Because mouth wash may influence the collection of samples, the patients will be instructed not to use mouth wash during the study. Blinding will be ensured by asking the patients to wash their hands before the examination, and the examiners will all wear the same mask, that will mask odors. The patients will also be asked not to drink, eat, chew gum, use mouth rinse or brush their teeth for at least 30 minutes before collection of oral samples, because of the influence it may have on the analytes.

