### 7.3.5 Dental Assessments

In the investigational sites with two or more dentists, a dentist will measure each periodontal disease parameter. In the investigational sites with one dentist only, a dentist will preferably measure these parameters, however, a trained hygienist could also do it.

From the moment the examiner meets the patient, blinding of the smoking status should be ensured, as described in section 6.4.1.

A single examiner at each site will perform all measurements throughout the whole study duration, if possible. A calibration session between examiners from different sites must be organized before V1.

Each site will need to develop a plan on how to ensure that they have properly qualified personnel, including back-up personnel necessary to conduct the required dental assessments. This will be documented in the delegation of authority log.

Unified periodontal probes will be used to ensure that all examiners will apply the same pressure when probing. The probe in this study will be PCPUNC15 (#30) by Hu-Friedy. Measurements will be rounded to the nearest millimeter (mm), based on visual judgement.

The dental assessments listed in the sections 7.3.5.1 to 7.3.5.8 below will be recorded on the prescribed periodontal charts.

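### The 30-minute rule before oral sampling omits smoking and IQOS use, so GCF and buccal samples at V3 and V4 may mix acute product effects with the effect of switching

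*Protocol*

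**What the plan says.** Protocol Section 6.5.6, for subgingival plaque, GCF and buccal samples at V2 to V4, reads: "patients will be asked not to drink, eat, chew gum, use mouth rinse or brush their teeth for at least 30 minutes before collection". The same list appears in Protocol Sections 4, 4.2, 7.5 and 9, in Appendix 1 footnote k, and in SAP Section 4.1. Section 4.2 explains that the rule exists "because of the influence it may have on the analytes".

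On the products themselves, Section 6.5.5 states: "There will be no restriction on allocated product use". Section 4.1 presents this as deliberate: an ad libitum "study without product use restriction in order to mimic as closely as possible" real-life conditions.

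On mechanism, Section 4.1 attributes the lower gingival inflammation, bleeding and GCF volume seen in smokers to nicotine, "probably due to the vasoconstrictive action of nicotine on gingival vessels". It also describes the buccal cells as directly exposed to smoke or aerosol.

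On blinding, Section 4.2 names as the threat "the smell of tobacco on patients using cigarettes, which is not present on patients using IQOS". Sections 4.2 and 6.4.1 answer it with a prescribed odour mask, hand washing, limited contact between examiner and patient, and a log of unblinding events. Data recorded after unblinding are kept (Protocol Section 6.4.1, SAP Section 4.3.2).

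**The concern.** The rule controls coffee, gum and toothpaste in the half hour before sampling because they might alter the analytes, yet leaves out the exposure that the trial compares. A patient who follows the protocol exactly may use a cigarette or a HeatStick minutes before giving GCF or a swab.

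The exploratory objectives are meant to show what three or six months of switching does to GCF mediators and the buccal transcriptome. If recent use leaves its own short-lived mark, and smoke and aerosol leave different marks, the group difference is a blend of acute and sustained effects. Without the time of last use, the two cannot be separated in the analysis.

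A secondary issue concerns the primary endpoint. The rule lapses once samples are taken, and the V3 and V4 periodontal examination follows. Nothing limits smoking shortly before that examination, and the protocol itself regards tobacco smell as a signal of group.

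**Working it through.** No arithmetic applies. The plan gives no figure for acute product effects or for odour-related bias, and the sample size in Protocol Section 12.2 does not depend on this point. The check is a comparison of passages.

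1. **Is product use covered anywhere?** The seven statements of the rule (Protocol Sections 4, 4.2, 6.5.6, 7.5, 9 and Appendix 1 footnote k; SAP Section 4.1) list food, drink, gum, rinsing and brushing. None lists smoking, IQOS or another nicotine product.

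2. **Is recency captured?** The diary is monthly (Protocol Section 7.5.7). Tables 4, 5 and 6 for V2, V3 and V4 contain no item for last use. The SAP's GCF model (Section 9.5.3) adjusts for average daily cigarette use at each visit, which measures quantity, not recency. The buccal analysis belongs to a separate SAP (SAP Section 3.3) that was not available.

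3. **Was timing considered elsewhere?** Yes, for urine: Section 4.1 relies on relatively long half-lives so that the hour of the visit should not matter. It makes no such argument for oral samples.

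4. **Which samples are exposed to a group difference?**

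| Visit | Samples relevant here | Product in use | Consequence of recent use |
|---|---|---|---|
| V2 | GCF, buccal swabs | Cigarettes in both arms (Protocol Section 6.2.1; Table 4 starts the allocated product at the end of the visit) | Noise in the baseline, no arm difference |
| V3 | GCF, buccal swabs | Allocated product | Acute smoke or aerosol effects may mix with the sustained effect |
| V4 | Buccal swabs | Allocated product | As at V3 |

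V2 is the GCF baseline (SAP Section 2.1.1), so noise there costs precision in the change score.

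5. **Which acute effects could differ between groups?** Section 4.1 expects IQOS to deliver nicotine at levels comparable to cigarettes. The vasoconstrictive effect should then arise in both groups and may largely cancel. What remains is any acute effect of smoke that differs from that of aerosol.

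6. **What about the examination?** Section 7.5 places sampling before the periodontal assessment. The 30-minute rule is tied to collection, so smoking is unrestricted both before sampling and between sampling and examination. The blinding safeguards act on the examiner, the hands and the record; none limits recent smoking.

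**The case against.** The strongest reply is that unrestricted use is the design. Recent use is part of real-life exposure, and no document shows that 30 minutes without product would be an adequate washout, since that interval was set for food, drink and hygiene. The second part stands, which is why recording the time matters as well as the pause. The first part carries less weight: a short pause at three visits does not alter six months of ad libitum use, and the same window already restricts ordinary eating and drinking.

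It is also fair to say that the affected endpoints are exploratory, that nicotine effects should be similar in both groups, and that the CRF and sample handling manual were not available. All of that stands. One can say that the protocol states no recording of last use, not that none takes place.

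Two stronger readings are tempting. A reader might infer that smoke odour is at its strongest when the blinded examiner measures PD. The documents do not support this: the examination comes after sampling and other visit procedures, nothing shows that patients smoke just beforehand, and the mask is prescribed specifically against odour. Nor is the 30-minute rule what removes rinsing as a remedy for odour, because Section 4.2 bars mouth wash for the whole study.

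A reader might also note that PD is read to whole millimetres (Section 7.3.5: "Measurements will be rounded to the nearest millimeter (mm), based on visual judgement") and derive a bias as a share of the 0.25 mm design difference. That needs the proportion of examinations unblinded, the proportion of readings altered and their direction. None is in the documents. The product would in any case be the total odour bias, not the part due to this omission.

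**Conclusion.** The omission is real and consistent across both documents, and it runs against the rule's stated purpose. It allows acute product effects into GCF at V3 and buccal swabs at V3 and V4; it does not show that they are there. Its size cannot be computed from the documents. The concern rests on two assumptions: that some patients use their product shortly before visits, and that smoke and aerosol have different acute effects on the analytes beyond nicotine.

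For the primary endpoint, the point is limited to an additional, unquantified odour risk to blinding at V3 and V4, which matters only if the existing safeguards fail. It does not establish that the PD comparison is biased. This is an inexpensive improvement that mainly serves the exploratory endpoints.

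**What to change.** - Add use of cigarettes, IQOS or any other tobacco- or nicotine-containing product to the existing 30-minute list in Protocol Sections 4, 4.2, 6.5.6, 7.5 and 9, Appendix 1 footnote k, and SAP Section 4.1. State that at V3 and V4 the window runs until the periodontal examination is finished. Reword Section 6.5.5 so that product use is unrestricted apart from this window.
- Record time and type of the last product used at V2, V3 and V4, and specify a sensitivity analysis of the GCF and buccal results that takes recency into account.
- Report the unblinding log by arm, and add a PD sensitivity analysis that excludes examinations logged as unblinded.

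The cost is a short pause in product use at three visits, one CRF field and the wording changes. The log is kept in the Site Investigator File, so its entries would also have to be brought into the analysis data.
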